8.1 Sample Size Considerations

This study is designed to assess the efficacy of the NanoKnife System with respect to the primary efficacy endpoint (12-month negative in-field biopsy rate), as well as to assess the safety of the NanoKnife System with respect to the primary safety endpoint (rate of adverse events).

Assuming that 69% of the subjects undergoing treatment with the NanoKnife System will have an in-field negative 12-month biopsy, a minimum of 51 intent-to-treat (ITT) subjects are required to achieve at least 80% power to conclude that the NanoKnife System's in-field negative biopsy rate is at least 52% (as summarized in [Table 2](#)).

The performance goal of 52% was based on the Sonablate 450 de novo summary (DEN150011), which reported a negative biopsy rate of 61% at 12 months (missing data imputed as positive), minus a 9% non-inferiority margin.

Table 2 Sample Size Determination

Endpoint	Primary Analysis Population	Assumed Performance of the NanoKnife System	Performance Goal	Non-Inferiority Margin	Power	Sample Size
12-month negative in-field biopsy rate	ITT	0.69	0.52	0.09	80%	51

For safety, it was determined that there is greater than an 80% chance to detect at least one medically significant adverse event if the true event rate is at least 1.6% with a sample size of 100 subjects.

Allowing for a possible 15% drop-out rate for subjects who will be lost to follow-up, a minimum of 118 subjects will be enrolled in the clinical study.

8.2 Eligibility Criteria

Subjects will be considered enrolled in the study after consent has been obtained.

Subjects will be assessed for inclusion into this study using the criteria identified below. Subjects must meet all inclusion criteria and not meet any exclusion criteria in order to qualify for the study.

8.2.1 Inclusion Criteria

A subject is required to fulfill all of the following criteria to be included in the study:

1. Is greater than 50 years of age;
2. Has at least a 10-year life expectancy;
3. Has histologically confirmed organ-confined prostate cancer, clinical stage \leq T2c;
4. Has a PSA \leq 15 ng/mL or PSA density < 0.15 ng/mL² if PSA is > 15 ng/mL;
5. Has Gleason score 3+4 or 4+3;
6. Has no evidence of extraprostatic extension by mpMRI;
7. Has no evidence of seminal vesicle invasion by mpMRI, and if suspected, confirmed by biopsy;
8. Physician is able to visualize prostate gland adequately on transrectal ultrasound imaging during qualifying biopsy;
9. Has a transperineal or transrectal targeted prostate biopsy of lesion, plus 10-14 core systematic biopsy to include adequate sampling of the peripheral zone correlating with an intermediate risk lesion¹ in the area of the MR-visible lesion;

¹ An intermediate risk lesion is defined as Gleason score 3+4 or 4+3, PSA < 15 ng/mL or PSA density < 0.15 ng/mL² if PSA is > 15 ng/mL, and \leq clinical stage T2c.

10. A visible lesion on mpMRI that is accessible to Irreversible Electroporation (IRE) treatment (Note: prostate cancer detected via systematic standard biopsy outside of the adjacent sextant location of the MRI visible lesion will meet entry criterion provided the positive core is Gleason 6; has fewer than 3 prostate biopsy fragments/cores positive and $\leq 50\%$ cancer in each of those fragments/cores on standard biopsy);
11. Is willing and able to sign a written informed consent form and in the judgment of the physician, the study is in the best interest of the subject;
12. Understands and accepts the obligation and is logistically able to present for all scheduled follow-up visits.

8.2.2 Exclusion Criteria

A subject will be excluded from the study if they meet any of the following criteria:

1. Has known hypersensitivity to pancuronium bromide, atracurium or cisatracurium;
2. Is unfit for anesthesia or has a contraindication for agents listed for paralysis;
3. Has an active urinary tract infection (UTI);
4. Has a history of bladder neck contracture;
5. Is interested in future fertility;
6. Has a history (within 3 years) of inflammatory bowel disease;
7. Has a concurrent major debilitating illness;
8. Had active treatment for a malignancy within 3 years, including malignant melanoma, except for prostate cancer or other types of skin cancer;
9. Has any active implanted electronic device (e.g., pacemaker);
10. Is unable or unwilling to catheterize;
11. Has had any prior or current prostate cancer therapy including:
 - a) Biologic therapy for prostate cancer;
 - b) Chemotherapy for prostate cancer;
 - c) Hormonal therapy for prostate cancer within three months of procedure;
 - d) Radiotherapy for prostate cancer;
 - e) Surgery for prostate cancer;
12. Has had prior transurethral prostatectomy (TURP), stricture surgery, urethral stent or prostatic implants;
13. Has had prior major rectal surgery (except hemorrhoids);
14. Is unfit for pelvic MRI scanning (e.g., severe claustrophobia, permanent cardiac pacemaker, metallic implants that are likely to contribute significant image artifacts, allergy or contraindication to gadolinium [to enhance MRI]);
15. Is actively bleeding, has a bleeding disorder, or is unable to interrupt blood thinning medications as clinically indicated per pre-operative best practices;
16. Is a member of a vulnerable population, such as cognitively impaired or incarcerated, that could expose them to undue influence, coercion, or inability to obtain informed consent;
17. In the opinion of the treating physician, has a contraindication listed in the current NanoKnife System User Manual (section 2.3).

9.0 Endpoints

9.1 Primary Endpoint

The primary treatment outcomes that will be evaluated are:

- Rate of negative in-field biopsy at 12 months – determine the rate of subjects obtaining a negative in-field biopsy on follow-up transperineal or transrectal biopsy at 12 months.
- Incidence of adverse events by type and Common Terminology Criteria for Adverse Events (CTCAE) v5.0 severity through 12 months – determine incidence, type, and severity during the NanoKnife System procedure and through follow-up.

9.2 Secondary Endpoint

The secondary outcomes that will be evaluated are:

- Rate of negative in-field biopsy at 12 months as defined by the Delphi consensus criterion of absence of clinically significant disease (≤ 3 mm of Gleason ≤ 6 disease in any biopsy core is insignificant) ([Postema et al., 2016](#)).
- Assessment of urinary function by comparison of pre- and post-operative UCLA-EPIC Urinary Domain ([Wei et al., 2000](#)), IPSS ([Barry et al., 1992](#)), and IPSS-QoL scores ([Rees, 2013](#)).
- Assessment of erectile function by comparison of pre- and post-operative IIEF-15 potency scores ([Rosen et al., 2002](#)).
- Effectiveness of therapy by measurement of PSA kinetics including time to PSA nadir.
- Assessment of changes in prostate volume by comparison of pre-treatment and 12-month prostate volume measured via mpMRI.
- Assessment of ablation effectiveness by evaluation of prostate tissue by mpMRI at 3 months post-treatment and at 12 months post-treatment.
- Assessment of need for secondary or adjuvant treatment following treatment with the NanoKnife System.
- Evaluation of subject reported pre- and post-operative QoL using the EQ-5D® ([Oppe et al. 2014](#)).

9.3 Population Sets

9.3.1 Screening Set (SS)

The SS comprises all subjects screened that are captured in the EDC. This set will be used only to report subjects' analysis sets.

9.3.2 Intent-to-Treat (ITT) Population

The ITT population includes all subjects who were enrolled and treated with the NanoKnife System. Any subject who has a NanoKnife probe inserted will be considered treated for the ITT population. The ITT population will serve as the primary analysis set for all safety and efficacy endpoints.

9.3.3 Per protocol (PP) Population

The PP population includes all subjects who were enrolled and treated with the NanoKnife System, and who had no major protocol deviations. The PP population will serve as a supportive analysis set for all efficacy endpoints.

10.0 Conventions and Derivations

10.1 Baseline Definition

Baseline visit is considered the visit between Screening and NanoKnife System treatment visits. However, Screening and Baseline visits may be combined.

Baseline assessments will be completed for all subjects who have completed all screening assessments and meet all inclusion criteria and none of the exclusion criteria. At the time the subject presents for baseline, an assessment will be made to determine whether the subject still meets the Inclusion/Exclusion criteria.

These baseline assessments must be completed within 30 days of treatment with NanoKnife System.

10.2 Adverse Events changing in severity/relationship with the treatment

All AEs which change in severity or relationship to NanoKnife System treatment are assigned a new start date and captured as a new record.

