12.8.1 Adverse Events

All AEs reported by the sites will be recorded in the EDC. All AEs that meet the criteria for adjudication will be reviewed by the adjudication committee. For the events that are adjudicated, the adjudicated data will serve as the primary data source for analysis purposes. The site-reported AE data will be used for analysis of AEs that do not meet the criteria for adjudication.

A summary of all AEs will be presented, including the number of events and number and percentage of subjects reporting adverse events in the following categories: any AE (including 95% CI for the proportion), any severe AE, any ADE, any AE leading to death, any SAE, and any AE leading to study discontinuation.

A

A breakdown of the number of events and the number and percentage of subjects reporting each AE, categorized by body system and preferred term coded according to the MedDRA dictionary, will be presented. Note that the counting of subjects with each event will be by subject rather than by event so that subjects are only counted once within each body system or preferred term.

A further tabulation of these data, categorized by relationship to NanoKnife System treatment, will be presented. When counting the number of subjects with each event, subjects with multiple events within a particular body system or preferred term will be counted under the category of their most procedure-related event within that body system or preferred term. Relationship to NanoKnife System treatment is categorized as: i) not related (“The cause of the AE is known and is not related to any aspect of study participation including the underlying condition”), ii) reasonably possibly related (“There is a reasonable possibility that the event may have been caused by study participation. The AE has a timely relationship to the study procedure(s); however, it follows no known pattern of response and an alternative cause seems more likely or there is significant uncertainty”), iii) probably related (“It is probable that the event was caused by study participation. The AE has a timely relationship to the study procedure(s) and follows a known pattern of response, but a potential alternative cause may be present.”), iv) definitely related (“The event was definitely related to study participation. A related event has a strong temporal relationship and an alternative cause is unlikely.”), or v) unknown as recorded on the CRF.

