A summary of events reported, categorized by severity (Mild [Grade 1], Moderate [Grade 2], Severe or medically significant but not immediately life-threatening [Grade 3], Life-threatening consequences [Grade

4], and Death [Grade 5]), will also be provided. Grades are determined according to CTCAE severity grades. When counting the number of subjects with each event, subjects with multiple events within a particular body system or preferred term will be counted under the category of their most severe event within that body system or preferred term.

All AEs recorded on the CRF will be provided in a listing. Independent listings will be provided with MedDRA system organ class (SOC), preferred and Verbatim terms for AEs, AEs with outcome of death, AEs leading to study discontinuation, and AEs related to NanoKnife treatment leading to study discontinuation.

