12.8.2 Deaths and Serious Adverse Events

Serious adverse events (SAEs) and NanoKnife System treatment-related SAEs will be summarized separately by body system and preferred term for the ITT subjects. All SAEs recorded on the CRF will be provided in a listing for subjects in the ITT population.

A table presenting the number of events and the number and percentage of subjects by body system and preferred term who experienced SAEs related to NanoKnife System treatment during the study will be presented for the ITT population. UADEs and deaths occurring in the study will also be listed for all subjects in the ITT population.

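### Each change in an AE's severity or relatedness becomes a new record, and no SAP rule stops one episode being counted several times in the descriptive event counts

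*Combined protocol and SAP*

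**What the plan says.** SAP 10.2, under Conventions and Derivations, consists of one rule: AEs whose grade or relatedness changes "are assigned a new start date and captured as a new record". It gives no identifier or other link between the old record and the new one.

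Three outputs name an event count:

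- **Overall AE summary (SAP 12.8.1):** "including the number of events and number and percentage of subjects reporting adverse events", with rows that cover any AE, any severe AE, any ADE and any SAE, among others.
- **Body system and preferred term (SAP 12.8.1):** "A breakdown of the number of events and the number and percentage of subjects reporting each AE".
- **Treatment-related SAEs (SAP 12.8.2):** "A table presenting the number of events and the number and percentage of subjects".

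The severity output is described as "A summary of events reported, categorized by severity". Its detailed counting rule concerns subjects, who are placed at their worst grade.

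The general rule against repeat counting is also for subjects: "the counting of subjects with each event will be by subject rather than by event so that subjects are only counted once". The relationship table has a matching rule, which places each subject at the most related event. Nothing equivalent is written for events.

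Protocol 6.1 also promises a table of AEs by maximum severity. Protocol 6.8 analyses the primary safety endpoint as the number and proportion of subjects with at least one AE, with a 95% confidence interval.

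**The concern.** Splitting a record when its grade changes is a legitimate way to keep the history of an event. The difficulty is what happens when the records are counted. One spell of haematuria that worsens and then settles is one clinical event, but under SAP 10.2 it is stored as several records, each with its own start date. Without a stated rule, a programmer cannot tell a continuation from a recurrence, and the natural count of events is the count of records.

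The distortion would be uneven. Protocol 5.1 follows AEs until they resolve, stabilise or the subject completes the study. The schedule has six post-treatment assessments (days 3 to 10, then months 1, 3, 6, 9 and 12). Long or fluctuating events therefore have several chances to be re-graded, and brief ones have few. Event totals by preferred term would partly reflect how often sites re-grade. In a single-arm study there is no control group with the same artefact to compare against.

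**Working it through.** **1. The plan's own safety figure.** SAP 8.1 and Protocol 6.2 claim more than an 80% chance of seeing at least one medically significant AE if the true rate is 1.6% with 100 subjects.

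- 1 − (1 − 0.016)^100 = 1 − 0.984^100 = 0.8007, so the claim reproduces.
- With 15% drop-out, 100 / 0.85 = 117.6, rounded up to 118, which also reproduces. With all 118 subjects the probability is 0.851.

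The calculation is per subject. The number of records per episode does not enter it.

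**2. Records per episode.** Each change opens one new record, so an episode with k changes gives k + 1 records. For E episodes, total records = E × (1 + mean changes per episode). The relative inflation of an event total equals the mean number of changes per episode.

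**3. One worked episode.** Take grades 1, 2, 3, 2, 1, so k = 4.

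| Count | Split records | Linked episode |
|---|---|---|
| Events, any grade | 5 | 1 |
| Events at Grade 1 / 2 / 3 | 2 / 2 / 1 | 0 / 0 / 1 |
| Subjects with the event | 1, at Grade 3 | 1, at Grade 3 |

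The subject row is unchanged. The event rows change in total and in mix: one of five records is severe (20%), whereas the single episode is severe.

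**4. Illustrative size.** The documents give no rate of change, so the shares below are assumptions. Records per 100 true episodes = 100 × (1 + share × changes).

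| Share of episodes that change | One change each | Two changes each |
|---|---|---|
| 10% | 110 | 120 |
| 20% | 120 | 140 |
| 30% | 130 | 160 |
| 50% | 150 | 200 |

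This table restates its inputs. It shows how the error scales and is not an estimate for this trial.

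**5. Which outputs are exposed.**

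- Overall AE summary, and body system and preferred term: event counts are explicit, so they are exposed.
- Severity table: exposed if events are tabulated, which the wording implies but does not state.
- Treatment-related SAEs: the event count is explicit, but SAP 10.2 is triggered by severity and relationship, not seriousness. A repeat count arises only if more than one record of the episode carries the serious flag (and is rated related), which the SAP leaves open.
- General SAE summary in SAP 12.8.2: no event count is named there. The any-SAE row of the overall summary does carry one, under the same condition on the flag.
- All subject counts and percentages, and the confidence interval: inflation is zero.

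**6. Maximum severity.** SAP 12.8.1 gives a worst grade per subject. Protocol 6.1 speaks of AEs. If that table is taken per AE, the split records must first be rejoined, and the SAP has no step for this. SAP 6.1, which lists departures from the protocol, does not mention it.

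**The case against.** The strongest reply is that SAP 10.2 concerns how data are captured. It does not say that a record is an event, so the reading that record counts will be printed as event counts is supplied by the reader. It is true that the SAP never defines an event. But the rule sits among the analysis conventions, it gives each new record its own start date, and nothing elsewhere says that an event is an episode. Counting records is what the text leads to.

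A second reply is adjudication. SAP 12.8.1 makes adjudicated data the primary source for events that meet the adjudication criteria. That may reduce the problem for those events, but no text says that adjudication merges split records, and the other AEs stay as reported by the site.

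A third reply concerns consequence, and it stands. A reader might infer that the primary safety endpoint is misstated, because it is worded as incidence of AEs by type and severity. The documents do not support that. Protocol 6.8 and SAP 12.8.1 attach the proportion and its interval to subjects, and subjects are counted once. No hypothesis, decision rule or sample-size statement uses event totals.

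A reader might also infer that every SAE and severity count is inflated. That goes too far as well, for the reasons in step 5 of the working.

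**Conclusion.** The point holds as a defect in descriptive event counts. As written, an episode with k changes in severity or relationship contributes k + 1 events to the overall AE summary and to the body-system and preferred-term table. The same applies to treatment-related SAEs if the serious flag is carried on more than one related record, and to the severity table if events are tabulated there. The SAP also lacks the re-linking step that a per-AE table by maximum severity would need.

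The primary safety analysis, all subject-level results and the 1.6% detection statement are untouched. The size of the inflation cannot be computed from the documents. It equals the mean number of changes per episode, and every percentage in the working rests on assumed rates. The conclusion also assumes that neither adjudication nor an undocumented programming convention merges the records. The change is worth making because event totals will be printed beside subject counts and read as part of the device's safety profile.

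**What to change.** In SAP 10.2 and 12.8:

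- Define an event as an episode.
- Link contiguous records of the same AE in the same subject under one episode identifier. Use a CRF link if one exists. Otherwise, require the same term and a new start date at or adjacent to the previous record's stop date.
- Count each episode once in every event count, at its maximum grade and closest relationship.
- Show the separate records in listings only.

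The same derivation supplies the Protocol 6.1 table of AEs by maximum severity.

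The cost is a short SAP paragraph and one derived variable. The documents do not show whether the CRF holds a link. If it does not, matching by term and date carries a small risk of merging a true recurrence where dates are partial or imputed under SAP 10.6.1. SAP 6.0 provides for a final version before database lock, which is the natural place for the change.

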10.3 Adverse Device Effects (ADEs) and Unanticipated Adverse Device Effects (UADE) Definition

Adverse device effects (ADEs) are a subset of adverse events (AEs). The ADEs are only those AEs caused by or related to the NanoKnife System. This definition includes any event resulting from insufficiencies or inadequacies in instructions for use, the deployment, or any malfunction of the device, including any event that is a result of a use error or intentional misuse.

An unanticipated adverse device effect (UADE) is any serious adverse effect on health or safety, any life-threatening problem or death caused by, or associated with a device, if that effect, problem, or death was not previously identified in nature, severity, or degree of incidence in the application; or any other unanticipated serious problem associated with a device that relates to the rights, safety, or welfare of subjects.

10.4 PSA Nadir Definition

PSA nadir is the absolute lowest level that PSA achieves after the initial NanoKnife System procedure up until the time of re-treatment, if applicable.

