10.6 Missing Data

Variables will be summarized for all eligible subjects with available data for the majority of endpoints/data (except for the endpoints/data detailed below). Missing data in the CRF will be detected by data management and monitored via edit checks and data analysis. Follow-up to collect missing data will be conducted as outlined in the Site Management Plan.

The following imputation methods will be applied:

- When calculating the proportion of subjects with a negative in-field biopsy, subjects with missing biopsy information post-ablation will be imputed as “positive”.
- Subjects with missing pre- or post-ablation prostate volume measurements will be imputed as having a zero change in volume. In accordance with the secondary endpoint related with “change in prostate volume”, this imputation will only be performed at Month 12 Visit.
- Missing PSA data will be imputed using last observation carried forward (LOCF).

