10.6.1 Imputation of Missing or Partial Dates

Partial or missing dates will be imputed only for adverse events, concomitant medication, and other dates required for analysis (e.g., Time to PSA nadir [months] is calculated as [date of PSA nadir– NanoKnife System Treatment date + 1]/30.25). For the purpose of date imputation, Visit 8 (i.e., 12 Months) is defined as the last available visit date. E.g., for PSA nadir, subjects who are not observed to have encountered the event at end of study are censored at date of last observation. In listings original (non-imputed) dates will be presented.

The following rules will be applied to impute missing or partial dates in appropriate data types:

Parameter	Missing	Additional Conditions	Imputation
Start date	D	M and Y of the event date are the same as M and Y of first NanoKnife treatment	Day of first NanoKnife treatment
		Y of the event date is before Y of first NanoKnife treatment and M of the event date is before M of first NanoKnife treatment	Last day of the month
		Y of the event date is before Y of first NanoKnife treatment but M of the event date is after M of first NanoKnife treatment	First day of month
		Y of the event date is after or the same as Y of first NanoKnife treatment but M of the event date is before M of first NanoKnife treatment	Last day of the month
		Y of the event date is after or the same as Y of first NanoKnife treatment and M of the event date is after M of first NanoKnife treatment	First day of the month
		Patient is not treated	First day of the month
	D and M	Y of the event date is the same as Y of first NanoKnife treatment	Day and month of NanoKnife treatment
		Y of the event date is before Y of first NanoKnife treatment	31 Dec
		Y of the event date is after Y of first NanoKnife treatment	01 Jan
		Patient was not treated	01 Jan
	M only	If D of the event date is present and M of the event date is not present, D of the event date will be treated as missing	See imputation rule for 'D and M'
	D, M, Y	None - date completely missing	Date of first NanoKnife treatment
Stop date	D	M and Y of the event date are the same as M and Y of end of study	Day of End of study
		Y of the event date is before Y of end of study and M of the event date is before M of end of study	Last day of the month
		Y of the event date is before Y of end of study but M of the event date is after M of end of study	First day of month

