12.7.5 Effectiveness of Therapy by Measurement of PSA Kinetics

The mean PSA levels at each visit, the overall percent reduction in PSA levels (ng/mL) from screening to each visit (1, 3, 6, 9, and 12 month follow-up), and the proportion of subjects with a PSA reduction compared to screening at each visit will be presented. If a subject is re-treated during the study, all PSA values collected following the re-treatment will not be included in the analyses but will be included in the listings. Mean PSA nadir and post-nadir PSA values through 12 months post-treatment will be summarized. Kaplan-Meier analysis and summary statistics for time, including median time to event and associated 95% CI will be presented for PSA nadir. For this assessment, our baseline will be the screening measurements.

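### Time to PSA nadir counts early leavers and re-treated subjects as having reached nadir while PSA may still be falling, and LOCF adds flat values to the post-nadir summary

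*Combined protocol and SAP*

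**What the plan says.** SAP 10.4 gives the definition: "PSA nadir is the absolute lowest level that PSA achieves after the initial NanoKnife System procedure up until the time of re-treatment". It asks for no later rise, no minimum follow-up and no threshold.

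SAP 12.7.5 sets the analysis: "Kaplan-Meier analysis and summary statistics for time, including median time to event and associated 95% CI will be presented for PSA nadir". It adds that "Mean PSA nadir and post-nadir PSA values through 12 months post-treatment will be summarized", and it drops PSA values collected after any re-treatment from the analyses while keeping them in listings.

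SAP 10.6.1 gives the time variable, (date of nadir − treatment date + 1)/30.25, and the censoring rule: "for PSA nadir, subjects who are not observed to have encountered the event at end of study are censored at date of last observation".

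SAP 10.6 gives the missing-data rule, with no exception for nadir or post-nadir summaries: "Missing PSA data will be imputed using last observation carried forward (LOCF". Protocol 6.4 has the same rule.

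Time to nadir and post-nadir stability are named in a secondary objective (protocol 3.3.2, SAP 7.2). Time to nadir is also named in a secondary endpoint (protocol 3.5.2, SAP 9.2). PSA is measured at months 1, 3, 6, 9 and 12 (protocol 4.6.16).

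**The concern.** The censoring rule expects some subjects to finish without reaching nadir, but the definition gives no way to identify them among subjects with PSA data. Any non-empty set of values has a lowest one. The subjects for whom censoring matters most, those lost or re-treated while PSA is still falling, enter as events at their last visit. The curve becomes the distribution of the visit with the lowest observed value, and early exit looks like early response.

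LOCF raises a related problem. A subject with no data after nadir can be given a run of identical values, which reads as stability in a summary meant to assess it.

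At stake is the description of PSA kinetics. The primary biopsy endpoint is not involved.

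**Working it through.** The documents give no figure for time to nadir or post-nadir PSA, so there is none to reproduce.

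**Step 1: who can be censored.** The event indicator is 1 whenever at least one post-treatment PSA exists before exit or re-treatment. The ITT population is anyone with a probe inserted (SAP 9.3.2), so it can include subjects with no post-treatment PSA. They are the only candidates for censoring. Even that is unsettled, because the SAP does not say whether LOCF may carry the screening PSA past treatment.

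**Step 2: what the rule does to one subject.** Suppose PSA falls at months 1 and 3 and the subject then leaves. With the last visit on day 90, time to nadir is (90 + 1)/30.25 = 3.0 months, coded as an event. Had PSA kept falling to a visit on day 365, it would have been (365 + 1)/30.25 = 12.1 months.

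**Step 3: size.** From the documents: the visit schedule, 15% drop-out and N = 118 (protocol 6.2, SAP 8.1). PSA trajectories are assumed; the documents give none.

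*Case A, PSA rises after nadir.* Assumed: true nadir uniform over months 2 to 9, then a log-PSA rise of 0.06 per month, log SD 0.15, drop-out spread evenly over visits. At 15% drop-out:
- About 3.5 of 118 have no post-treatment PSA; the other 97% have the event.
- About 14.1 have their lowest value at their last observed visit, of whom 4.1 are at month 12. So about 14.1 − 4.1 = 10 early leavers are coded as events at their last visit.
- Mean time to nadir is 5.78 months against 6.08 with full data, a shift of 0.30. The median stays at 6.0 in both, because nadir can fall only on a few visit dates.
- At 30% drop-out plus 5% missed visits, the mean is 5.49 against 6.08.

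*Case B, no rise after nadir.* Assumed: PSA falls to 30% of baseline by month 6, 9 or 12 and then stays level, log SD 0.15, 15% leave early.

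| Floor reached at | Leavers with lowest value at last visit | Mean, all followed | Mean, 15% leave | Shift |
|---|---|---|---|---|
| Month 6 | 87% | 8.99 | 8.30 | 0.69 |
| Month 9 | 96% | 10.48 | 9.60 | 0.88 |
| Month 12 | 92% | 11.76 | 10.68 | 1.08 |

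**Step 4: LOCF, under Case A.** At 15% drop-out about 15% of post-nadir visit values are imputed. About 9% of subjects with a nadir before month 12 have an entirely imputed, flat post-nadir course. The mean rise from nadir to month 12 is 1.171 ng/mL with LOCF against 1.226 with full data: 1 − 1.171/1.226 = 4.5% smaller. At 30% drop-out plus 5% missed visits it is 0.985 against 1.120: 1 − 0.985/1.120 = 12% smaller. With nothing missing, LOCF has no effect.

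**The case against.** **The endpoint is bounded at 12 months.** Protocol 4.6.16 and SAP 12.7.5 look at PSA through 12 months. On that reading, a completer whose lowest value is at month 12 has reached the 12-month nadir, and requiring a confirmed later rise would be a different estimand. This stands. It is why month-12 completers should not be treated as having no nadir in the main analysis.

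**A large share without nadir.** If every subject whose lowest value is the last one were censored, 35%, 52% and 91% would be without nadir after month 12 in Case B, against 0% as written. A reader might take this as the size of the defect, but it is not. With no drop-out at all the same rule gives 33%, 50% and 92%, so nearly all of it comes from completers. It also depends on assuming no rise: adding 0.03 per month to the month-6 case takes it from about 35% to 14%, and 0.06 takes it to 4%.

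**LOCF after re-treatment.** A reader might infer that LOCF fills visits after re-treatment. No section says so. SAP 10.4 ends nadir at re-treatment, SAP 12.7.5 excludes later values, and SAP 12.1 uses data up to re-treatment for subjects who then exit. Truncation is the natural reading, and the point needs only a clarifying sentence.

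**Importance.** Protocol 6.2 says the study is not powered for secondary claims, and SAP 12.7.5 plans no hypothesis test on PSA. This limits the weight of the point. It does not remove the bias in a named endpoint.

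**Conclusion.** The point holds in a limited form. Censoring can reach at most subjects with no post-treatment PSA. Subjects who exit or are re-treated early with PSA still falling are counted as events at their last visit, which biases time to nadir towards earlier values and leaves their incomplete follow-up out of the CI. At 15% drop-out the mean shift is about 0.3 months in Case A and 0.7 to 1.1 months in Case B. In Case A the reported median did not move. LOCF biases the stability summary in proportion to missingness, by about 4-5% of the post-nadir rise at 15% drop-out in Case A. All of these sizes rest on assumed trajectories.

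Two stronger readings are not supported. The first is that every subject has the event and censoring never applies: an ITT subject with no post-treatment PSA has no nadir, unless screening PSA is carried forward, which the SAP leaves open. The second is that LOCF makes post-nadir PSA flat as a whole: it touches only missing values, and observed ones are summarized as measured.

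**What to change.** In SAP 10.4 and 10.6.1:
- Derive nadir, time to nadir and post-nadir summaries from observed PSA only, and state that no value is carried past re-treatment.
- For time to nadir, censor at the last observed PSA any subject who exits or is re-treated before month 12 with the lowest value at that visit.
- For completers whose lowest value is at month 12, keep it as the nadir within 12 months, report their number separately, and censor them in a sensitivity analysis.

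In SAP 12.7.5, keep the LOCF by-visit PSA summaries and show observed-value summaries beside them. List the departure from the protocol's LOCF rule in SAP 6.1.

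The cost is SAP wording and programming before database lock, with no new data. There will be slightly fewer events and a wider CI. Censoring early leavers may be informative, since exit or re-treatment can be related to the course of PSA, and the report should say so.
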